Specific to Genetics protections: No one other than study staff will have access to the blood. Blood samples will be coded with no subject identifiers according to the procedures of the Center for the Studies of Addiction. The genetic testing laboratory will not have access to your name, and all information will be stored in restricted areas and locked cabinets. Subjects will be identified by number only on the computerized database. As part of consent procedures, subjects will be advised of the precautions taken to preserve confidentiality. DNA samples will be stored in a laboratory at The Center for Neurobiology at the University of Pennsylvania. Access to stored samples will be limited to approval by [name] [contact]) or her designee. Future studies involving stored DNA samples must receive University of Pennsylvania approval and will be limited to studies related to addictions. DNA samples will not become part of the clinical record and will not be made available for commercial use.

2. Potential Study Benefits

Subjects may benefit from the close medical monitoring, which may assist in quitting smoking. In comparison, the benefits to society in gaining knowledge about the brain substrates involved in tobacco dependence are great. The studies are well grounded in pre-clinical research literature, hypothesis-driven, and employ state-of-the-art instruments and expertise. Important and significant contributions to drug addiction research are substantial and outweigh the few (well-managed) risks in the study.

3. Alternatives to Participation

Regardless of the reason, if an individual interested in smoking reduction/cessation help does not participate in this study, he or she may be informed of non-research smoking reduction/cessation programs available within the Penn Health System or around Philadelphia. These individuals may also be informed of other available smoking help options (e.g. NRT, American Cancer Society programs, etc.).

4. Management of Information for Multi-center Research where a Penn Investigator is the Lead Investigator of a multi- center study, or Penn is the lead site in a multi-site study.

N/A

5. Risk/Benefit Assessment

Risks associated with this project are minimal because of the described protections that will be implemented. Subjects may benefit from the close medical monitoring, which may assist in quitting smoking. In comparison, the benefits to society in gaining knowledge about the brain substrates involved in tobacco dependence are great. The studies are well grounded in pre-clinical research literature, hypothesis-driven, and employ state-of-the-art instruments and expertise. Important and significant contributions to drug addiction research are substantial and outweigh the few (well-managed) risks in the study.

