Exposure to smoking cues will not affect how 10-repeats smoke a cigarette whereas 9-repeats will smoke more of their cigarette following cue exposure, as measured by solanesol content.

During-medication outcome variables:

Following 3 weeks of medication, measures of anxiety and depression may be reduced in baclofen-treated subjects compared to placebo-treated subjects, as evinced by lower scores on the HAM-D and HAM-A.

Throughout treatment, alcohol/other drug craving and use may be reduced in baclofen-treated subjects compared to placebo-treated subjects as measured by lower scores on the Alcohol Urge Questionnaire (AUQ) and reduced days of use as measured by the Time-Line-Follow-Back (TLFB).

Baclofen-treated subjects will show differences in how they evaluate their last cigarette smoked as measured by the modified Cigarette Evaluation Questionnaire (mCEQ).

Post-medication outcome variables

Following the 3-week imaging paradigm and 5 additional weeks of treatment, subjects treated with baclofen will have better treatment outcome, as evinced by reductions in urine cotinine levels, and cigarettes smoked per day compared to placebo-treated subjects, as measured by urine cotinine levels and cigarettes smoked per day.

Females who begin treatment in the follicular phase of the menstrual cycle and who are baclofen-treated will have better treatment outcome than females who begin treatment in the luteal phase who are baclofen-treated, as evinced by reductions in urine cotinine levels, and cigarettes smoked per day.

BACKGROUND and SIGNIFICANCE

The Problem is Relapse, motivated by Craving Cigarette smoking is the leading cause of preventable death in the nation and is the direct cause of 87% of lung cancer cases, as well as chronic obstructive pulmonary disease, emphysema and myriad other devastating and fatal diseases. Of the roughly 36 million smokers in the nation, most desire to quit, and 40% make an attempt each year, while less than 5% succeed (1, 2). The deleterious effects of smoking highlight the importance of identifying the genetic underpinnings and the brain targets that will aid in identifying effective treatments that will improve treatment outcomes.

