Besides smoking cue exposure and withdrawal other factors are involved in smoking behaviors such as continued smoking, craving and relapse. These include attention problems – nicotine enhances attention and some smokers smoke to improve attention (100); menstrual cycle phase – because of the enhanced discomfort of pre-menstrual cycle symptoms and decreased self-efficacy, menstrual cycle phase at start of treatment can affect treatment outcome (6); ability to label feelings – we hypothesize that the inability to label the craving state could be a relapse vulnerability (32); drinking alcohol – drinking alcohol reduces inhibition and often leads to relapse to cigarette smoking (9). Thus, additional measures will be acquired in this protocol that will provide data towards these potential mitigating factors.

CHARACTERISTICS OF THE STUDY POPULATION

1. Target Population:

Patients will be 100 randomized physically healthy and mentally stable male and non-pregnant female patients between the ages of 18 and 60 who smoke 6 or more cigarettes per day for at least 6 months. Subjects will not be excluded based on gender, religion, race, or socioeconomic status. The subject population of previous smoking studies in our lab was 54% female, 62% Caucasian and averaged 15 years of education. This is representative of the urban population in the northeast region of the United States who seek help for nicotine dependence. We expect our current population to have similar characteristics. Thus, women and minorities will be well represented in our study. No special subject groups are included in the protocol.

2. Accrual: 100 randomized (we expect 15 subjects to be lost to attrition)

3. Inclusion Criteria:

- 1) Physically healthy, as determined by a comprehensive physical examination and approval of the study physician males or females who smoke cigarettes, ages 18-60.
- 2) Smoke \geq 6 cigarettes per day for at least 6 months prior to study start date.
- 3) Females must be non-pregnant, non-lactating and either be of non-childbearing potential (i.e. sterilized via hysterectomy or bilateral tubal ligation or at least 1 year post-menopausal) or of child bearing potential but practicing a medically acceptable method of birth control. Examples of medically acceptable methods for this protocol include barrier (diaphragm or condom) with spermicide, an intrauterine device (IUD), the Nuvaring, oral contraceptives, levonorgestrel implant, hormonal injection or complete abstinence.

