Hemoglobin
Hematocrit
MCV
MCH
MCHC
RDW
Platelets

Measures acquired at the Physical Examination Visit

Smoking History Assessment Demographics, family history, smoking topography and severity of nicotine dependence is determined from a laboratory-developed Smoking History Questionnaire (SHQ) that includes the **Fagerstrom Test for Nicotine Dependence (FTND)**. The FTND is a 6 item, self-report measure of nicotine dependence derived from the Fagerstrom Tolerance Questionnaire. Internal consistency of the FTND scale is satisfactory (Cronbach's alpha - .64), and it has a high test-retest reliability (re = .88). Demographics and smoking history assessments are necessary for characterizing the population and publication. (administration time: approximately 5 min)

Reasons for Smoking Questionnaire (RSQ), is a 34 item, 4-point likert-scale, self-report measure probing the underlying motivations for smoking. Individual reasons underlying smoking behavior (e.g., to reduce WD symptoms, SC exposure, stress) will be used in conjunction with brain and genetic data to learn more about individual smoking behavior that will eventually be helpful in planning personalized smoking cessation strategies. (administration time: approximately 4 mins)

Toronto Alexithymia Scale (TAS-20) is a widely used and psychometrically valid instrument to measure alexithymia. It is a self-report questionnaire containing 20 items (e.g., I am often confused about what emotion I am feeling) rated on a 5-point scale from strongly agree (1) to strongly disagree (5). A high score (>62) indicates a high degree of alexithymia. Scoring on this questionnaire is interpreted using a three-factor solution: factor 1 items reflect difficulty identifying feelings, factor 2 items reflect difficulty describing feelings, factor 3 items reflect externally-oriented thinking. This measure is being acquired because we have found that symptoms of alexithymia may be modulated by DAT genotype and higher symptoms may be found in 9-VNTR smokers. We are collecting this measure to test this hypothesis. (administration time: approximately 3 min)

Menstrual Cycle Questionnaire (MCQ) This questionnaire will be administered by the Nursing Staff to all female prospective subjects during the physical evaluation. It elicits information on menses status, menstrual cycle length, and premenstrual symptoms (PMS). This measure is acquired because we have found that menstruating females

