who are in the luteal phase of the cycle crave more during smoking cue exposure (101), do poorly in treatment (6, 102), and have greater brain responses to smoking cues (103) compared to follicular phase females. Further, it is acquired because symptoms of PMS and withdrawal are poorly distinguished (104). The questionnaire is designed to distinguish symptoms that are clearly PMS from those that are clearly withdrawal. In this way, we will have information that will help us determine whether potential symptoms are related to withdrawal or PMS. Further, we have observed that the brain responses of females who are post-menopausal differ during smoking cue exposure compared to menstruating females, perhaps revealing different underlying relapse vulnerabilities. This questionnaire (and progesterone/estrogen levels) will help us determine if females are pre-, peri- or post-menopausal [administration time: 1-3 min (this varies depending on whether subject menstruates)].

4. Psychological Evaluation Visit (1 to 1.5 hours)

The following evaluations will be completed by a trained clinician:

MINI International Neuropsychiatric Interview (MINI): This is a short and accurate structured diagnostic psychiatric interview. It will be used to determine current DSM-IV diagnosis of any psychoactive substance dependence other than nicotine. Nicotine dependence is often accompanied by other drug dependencies. It will also be used to diagnose current severe psychiatric symptoms, e.g., psychosis, dementia, acute suicidal ideation, mania or depression requiring antidepressant therapy, or which would make it unsafe for the subject to participate in the opinion of the primary investigators. The MINI has excellent inter-rater reliability and very good test-retest reliability. Prior to completion of the MINI, the administering clinician will review the subject's reported history, in addition to any prohibited medications. Since the MINI does not evaluate for acute homicidal ideation, we have referenced such a question from another study within our center and have included it in our procedures. (administration time is approximately 30 minutes).

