Modified Cigarette Evaluation Questionnaire (mCEQ): Assesses the degree to which subjects experience the reinforcing effects of smoking. It is a standardized, validated and reliable measure with multi-item domains on smoking satisfaction, psychological reward and aversion and craving reduction. Confirmatory factor analysis exceeds 0.90. Baclofen has been shown to modify how one assesses smoking (105). This might be one mechanism underlying its potential efficacy. The mCEQ will be administered to assess the effects of baclofen on the evaluation of subject's last cigarette. (administration time: approximately 3 mins)

Blood: On scan days, all females will provide a blood sample (approx.. 2 tablespoons) for biochemical verification of cycle phase. Bloods will be tested for levels of progesterone and estradiol.

Urine Pregnancy Test: All females of childbearing potential will be assessed for pregnancy with a urine test prior to being allowed to participate in the MRI.

Urinalysis: Urines are analyzed for cotinine, the primary metabolite of nicotine, at this visit, Scan Day 2 and also at the Week 8 visit. Cotinine levels correlate with nicotine intake, which will aid in determining changes in smoking behavior. In addition, the urine sample from Scan Day 1 and 2 will be tested on-site for the presence of illicit substances. A positive result will lead to the cancellation of the scan and the exclusion of the subject from further study participation.

Cigarette filters for solanesol testing: Cigarette filters will be collected and analyzed for solanesol, a naturally occurring substance present in tobacco that provides a precise measurement of smoke exposure.

Alcohol Craving Measures – It has been shown (see Background and Significance section above) that baclofen reduces craving and relapse in alcohol dependence. Subjects in this study are not alcohol dependent, but they have varying amounts of use. Since drinking alcohol and smoking often go hand in hand, we have added the following two measures to examine whether baclofen reduces alcohol urges and/or drinking.

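### The menstrual-phase hypothesis compares women within the baclofen arm only, so it cannot separate prognosis from a phase-specific response to baclofen

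*Combined protocol and SAP*

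**What the plan says.** The hypothesis is in Objectives, Secondary Outcome Variable(s), under the post-medication outcomes: "Females who begin treatment in the follicular phase of the menstrual cycle and who are baclofen-treated will have better treatment outcome". The group they are set against is luteal-start women who also receive baclofen. The outcomes are reductions in urine cotinine and in cigarettes per day. The item directly before it, on the same two outcomes, compares baclofen with placebo.

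Two other places describe phase as a predictor of outcome:

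- Under Other factors involved in smoking behavior: "menstrual cycle phase at start of treatment can affect treatment outcome (6".
- Under Menstrual Cycle Questionnaire (MCQ), of women in the luteal phase: "do poorly in treatment (6, 102), and have greater brain responses to smoking cues (103) compared to follicular phase females".

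Neither statement mentions baclofen.

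Phase information is collected whatever the treatment. Of the MCQ the plan says: "This questionnaire will be administered by the Nursing Staff to all female prospective subjects during the physical evaluation". For hormone levels: "On scan days, all females will provide a blood sample".

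The Analyses section gives no model for phase, no comparison of phase with placebo women included, and no phase-by-treatment term. Randomization is by sex and DAT genotype, not by phase. For DAT genotype, by contrast, Aim 3 names a 2 x 2 design and an interaction with treatment.

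**The concern.** A claim that follicular-start women respond better to baclofen is a claim about effect modification: the baclofen-placebo difference is larger in one phase than in the other. The stated contrast looks only at the treated side. If follicular-start women do better in any quit attempt, they will do better on baclofen even if the drug is inert.

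The plan's own background makes that alternative a live one. A significant difference could then be reported as a phase-specific baclofen response, and could guide the timing or selection of treatment in later work, when only prognosis differed between the groups.

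**Working it through.** The plan states no sample size, effect size or power for this contrast, so there is no figure to reproduce. The check asks how often the stated contrast would be positive if baclofen had no phase-specific effect at all.

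**Inputs from the document**
- 100 randomized, 15 expected lost (Accrual): 85 evaluable.
- 54% women in the group's earlier studies, with a similar population expected (Target Population).
- 2 baclofen to 1 placebo (Randomization).
- Alpha 0.05 (Behavioral Analyses). Sidedness is not stated; two-sided is assumed.

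**Assumptions not in the document**
- 60-100% of women are cycling. 100% is a ceiling, because eligibility runs to age 60 and admits post-menopausal and surgically sterilized women and users of hormonal contraception.
- Follicular and luteal starts are equally common.
- Phase shifts the outcome by d = 0.3, 0.5 or 0.8 SD, identically in both arms.

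**Group sizes**
- Women: 85 x 0.54 = 45.9.
- Baclofen: 45.9 x 2/3 x (0.6 to 1.0) = 18.4 to 30.6, or 9.2 to 15.3 per phase.
- Placebo: 45.9 x 1/3 x (0.6 to 1.0) = 9.2 to 15.3, or 4.6 to 7.7 per phase.

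**Standard errors (outcome SD = 1)**
- Within the baclofen arm: sqrt(4/nB) = sqrt(4/18.4) = 0.47 to sqrt(4/30.6) = 0.36.
- Phase-by-arm interaction: sqrt(4/nB + 4/nP) = sqrt(4/18.4 + 4/9.2) = 0.81 to sqrt(4/30.6 + 4/15.3) = 0.63.
- Ratio: nP = nB/2, so sqrt(1 + 2) = 1.73.

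**Probability of a significant result with no baclofen-by-phase effect** (two-sample t-test, noncentrality d/SE)

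| Phase effect, same in both arms | Within-baclofen contrast, 60% cycling | Within-baclofen contrast, 100% cycling | Interaction test |
|---|---|---|---|
| 0.3 SD | 9% | 13% | 5% |
| 0.5 SD | 17% | 27% | 5% |
| 0.8 SD | 36% | 57% | 5% |

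A simulation of 20,000 trials per scenario, with cells of 15 and 15 on baclofen and 8 and 8 on placebo, gave 13%, 26% and 56% for the within-arm contrast. The interaction test stayed between 4.95% and 5.15%.

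**Sensitivity.** Using all 100 randomized (54 women, 36 on baclofen), all cycling, a normal approximation gives 15%, 32% and 67%. The same approximation at 85 evaluable gives 13%, 28% and 60%. A 40:60 phase split in place of an equal one, at 85 evaluable and all cycling, gives 13%, 27% and 58%.

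**Price of the interaction.** By the normal approximation, the difference detectable with 80% power at 85 evaluable, all cycling, is (1.96 + 0.84) x 0.36 = 1.01 SD within the arm and (1.96 + 0.84) x 0.63 = 1.75 SD for the interaction (from unrounded standard errors).

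**The case against.** The strongest reply is that the sentence, read literally, says only that among baclofen-treated women the follicular starters will do better. That can be true and purely prognostic. The plan lists it as an expected outcome, prescribes no test, and elsewhere groups phase with potential mitigating factors, not with markers of drug response. This stands in part. A reader might infer that the sponsor intends to read a positive result as a baclofen effect, but the documents do not say how the result will be interpreted. What can be said is that the contrast leaves that reading open and cannot support it.

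A second reply concerns the background. A reader might infer that the plan asserts a follicular advantage on placebo. It does not. By its listed title, one cited source is a retrospective analysis of a nicotine-replacement trial, and the other presents a hypothesis about discordant findings. A shared effect in both arms is a reasonable inference from unqualified statements, not a stated fact. The argument needs only that the contrast cannot rule it out.

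Third, no phase effect size appears in the documents, so the percentages are illustrative and those at 100% cycling are ceilings. This stands. The logical gap does not depend on them.

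Fourth, the interaction test has little power. For an interaction of 0.5 SD its power is only about 9-12%. This also stands, and it is a reason to label the result exploratory. It does not make the one-arm contrast informative about baclofen.

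Finally, a reader might extend the criticism to the solanesol hypothesis, which predicts that "Exposure to smoking cues will not affect how 10-repeats smoke a cigarette" while 9-repeats will smoke more. The documents do not support that extension. The Design section already states a between-genotype comparison of cigarette consumption after cue exposure, and nowhere are separate within-genotype tests prescribed or a non-significant result equated with no effect.

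**Conclusion.** The point holds in this form: the contrast omits placebo women, the plan describes phase as related to outcome without tying that to baclofen, and no later section supplies the missing comparison. A positive result could reflect prognosis alone and cannot establish a phase-specific response to baclofen. Under the assumptions set out above, a prognostic phase effect by itself would make the contrast significant in about 9-13%, 17-27% or 36-57% of trials, depending on whether that effect is 0.3, 0.5 or 0.8 SD. The stronger statement that the trial would misreport prognosis as a drug effect goes beyond the text. The primary aims are unaffected.

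**What to change.** Do one of two things.

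1. If a phase-specific response to baclofen is the question, use all randomized cycling women. Estimate the follicular-luteal contrast in each arm, report the baclofen-placebo difference within each phase, and report the phase-by-arm interaction, all with confidence intervals and labelled exploratory. State in advance how phase at treatment start is assigned from the questionnaire and the hormone levels.
2. If prognosis is the question, restate the hypothesis as prognostic and include both arms.

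Either way the change is to wording and analysis, since phase data are already collected from all women. The cost of the first option is precision: the interaction SE is about 0.63-0.81 SD, about 1.7 times that of the within-arm contrast. Only a very large difference could be shown, and the claim becomes weaker.
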